### All B/F/TAF Analysis:

- For subjects who receive B/F/TAF in the randomized phase, all available data collected from both randomized phase and OL extension phase (if applicable) will be included in the all B/F/TAF analysis.
- For subjects who receive DTG + F/TAF in the randomized phase and receive at least 1 dose of B/F/TAF in the extension phase, (1) all available AE, concomitant medication, pregnancy, and death data with start date **on or after** the first dose date of B/F/TAF in the extension phase and (2) all available other data, such as laboratory, vital sign, and ECG data, collected **after** the first dose date of B/F/TAF in the extension phase will be included, except that the data collected **on or prior to** the first dose date of B/F/TAF will be used to derive the baseline value for the all B/F/TAF analysis.

Note that all data for subjects who receive DTG + F/TAF in the randomized phase and do not receive any dose of B/F/TAF in the extension phase will be excluded from all B/F/TAF analysis. The actual treatment received will differ from the randomized treatment only when the actual treatment received differs from randomized treatment for the entire treatment duration.

Analysis results will be presented using descriptive statistics. For categorical variables, the number and percentage of subjects in each category will be presented; for continuous variables, the number of subjects (n), mean, standard deviation (SD) or standard error (SE), median, first quartile (Q1), third quartile (Q3), minimum, and maximum will be presented.

All statistical tests will be 2-sided and performed at the 5% significance level unless otherwise specified.

By-subject listings will be presented for all subjects in the All Randomized analysis set unless otherwise specified, and sorted by subject identification (ID) number, visit date, and time (if applicable). Data collected on log forms, such as AEs, will be presented in chronological order within a subject. The treatment group to which subjects were randomized will be used in the listings.

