# 3.2. Subject Grouping

For the randomized phase analyses using the All Randomized Analysis Set or the FAS, subjects will be grouped by the randomized treatment (labeled as B/F/TAF vs. DTG + F/TAF). For all other randomized phase analyses, subjects will be grouped by the actual treatment received. The actual treatment received will differ from the randomized treatment only when the actual treatment received differs from randomized treatment for the entire treatment duration.

For all B/F/TAF analyses, subjects will be grouped into the following 3 groups:

- B/F/TAF group: This group includes all subjects who actually received B/F/TAF in the randomized phase of this study, regardless whether subjects receive any B/F/TAF in the extension phase or not.
- DTG + F/TAF to B/F/TAF group: This group includes all subjects who actually received DTG + F/TAF regimen in the randomized phase of this study and then receive at least 1 dose of B/F/TAF in the extension phase
- All B/F/TAF group: This group includes all subjects who actually received at least 1 dose of B/F/TAF in either phase. This group includes the B/F/TAF group and the DTG + F/TAF to B/F/TAF group. Only data collected on and after the first dose date of B/F/TAF may be included.

Treatment comparisons will only be made between B/F/TAF and DTG + F/TAF for the randomized phase analysis.

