## 7.1.5. Treatment-Emergent Adverse Events

## 7.1.5.1. Definition of Treatment-Emergent Adverse Events

Treatment-emergent adverse events (TEAEs) are defined as 1 or both of the following:

- Any AEs with an onset date on or after the study drug start date and no later than 30 days after permanent discontinuation of the study drug, or
- Any AEs leading to premature discontinuation of study drug.

More specifically, the AE onset date will be compared with the first and last randomized study drug dates for the randomized phase analysis. For the all B/F/TAF analysis, the AE onset date will be compared with the first and last study drug dates.

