#### 7.4.2. Concomitant Non-ARV Medications

Concomitant non-ARV medications (ie, medications other than study drug that are taken while receiving study drug) will be coded using the WHO Drug Dictionary. The WHO Drug preferred drug name and drug code will be attached to the clinical database. Use of concomitant medications from Study Day 1 up to the last dose date will be summarized (number and percentage of subjects) by treatment group and preferred drug name based on the Safety Analysis Set for randomized phase analysis and All B/F/TAF Analysis Set for all B/F/TAF analysis, respectively. Multiple drug use will be counted only once per subject for each preferred drug name. The summary will be sorted by decreasing total frequency. For drugs with the same frequency, sorting will be done alphabetically.

If the start or stop date of non-ARV medications is incomplete, the month and year (or year alone if month is not recorded) of the start or stop date will be used to determine whether the non-ARVs are concomitant or not. The medication is concomitant if the month and year of the start or stop (or year of the start or stop, if month is not recorded) of the medication does not meet either of the following criteria:

- The month and year of start of the medication is after the date of the last dose of study drug
- The month and year of stop of the medication is before the date of the first dose of study drug

If the start and stop date of non-ARV medications are complete, the start date is not after last dose date and the stop date is not before first dose date, or the non-ARV medications are marked as ongoing and start date is on or before last dose date, the non-ARV medications are concomitant. For the randomized phase analysis, Study Day 1, the first and last dose dates refer to Study

Day 1, the first dose date and the last dose date defined for the randomized phase analysis. For the all B/F/TAF analysis, Study Day 1, the first and last dose dates refer to Study Day 1, the first dose date and the last dose date defined for the All B/F/TAF analysis.

Summaries of non-ARV concomitant medications will be provided based on the Safety Analysis Set for randomized phase analysis and All B/F/TAF Analysis Set for all B/F/TAF analysis, respectively. Subjects with any non-ARV concomitant medications will be listed. No inferential statistics will be provided.

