# 19) Lipid modifying medication analyses:

- Lipid modifying medication is defined to be the concomitant medication with WHO Drug ATC2 term (drug class) = "LIPID MODIFYING AGENTS" and WHO Drug preferred drug name (CMDECOD) contains wording of "STATIN" in the ADCM dataset.
- Subjects who took lipid modifying medications at study entry refer to the subjects who have any use of the lipid modifying agents at study day 1 (ie, the first dose date) for randomized phase analysis.
  - a) More specifically, subjects with "Lipid Modifying Agent Use at Study Entry" include those subjects in safety analysis set for randomized phase analysis with meeting both the following criteria: 1) any selected CM record with the start date ≤ the first dose date for randomized phase analysis, and 2) the end date of the selected CM record ≥ the first dose date or the end date of the selected CM record is ongoing
  - b) For lipid modifying medications with the start date completely unknown, we assume the start date is on or before the first dose date, lipid modifying medication was considered as being taken at study entry if the end date is not prior to the first dose date (ie, the end date is on or after the first dose date, completely unknown, or ongoing).
  - c) Lipid modifying medications with the start date prior to the first dose date for randomized phase analysis and the end date unknown (completely missing) were considered as being taken at study entry (the unknown end date is assumed on or after the first dose date).
- Subjects who initiated lipid modifying medications during the study for randomized phase analysis refer to the subjects in the safety analysis set who didn't take lipid modifying medications at study entry and with any selected CM record started after the first blinded study drug dose date and on and prior to the last blinded study drug dose date.
- Subjects who took lipid modifying medications at first dose of B/F/TAF (including both phases) refer to the subjects who use of the lipid modifying agents at study day 1 of all B/F/TAF analysis. More specifically, subjects with "Lipid Modifying Agent Use at

First Dose of B/F/TAF" include those subjects in All B/F/TAF Analysis Set with: 1) any selected CM record with the start date ≤ the first dose date of B/F/TAF (including both phases), and 2) the end date of the selected CM record is ongoing or the end date of the selected CM record ≥ the first dose date of B/F/TAF (including both phases).

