- a) For lipid modifying medications with start date completely unknown, we assume the start date is on or before the first dose date of B/F/TAF (including both phases), lipid modifying medication was considered as being taken at first dose of B/F/TAF (including both phases) if the end date is not prior to the first dose date of B/F/TAF (including both phases) (ie, the end date is on or after the first dose date of B/F/TAF (including both phases), completely unknown, or ongoing).
- b) Lipid modifying medications with the start date on or prior to the first dose date of B/F/TAF (including both phases) and the end date completely unknown were considered as being taken at first dose of B/F/TAF (including both phases).
- Subjects who initiated lipid modifying medications while subject receiving B/F/TAF includes the following subjects in the All B/F/TAF Analysis Set: (1) for subjects who permanently discontinued study drug with any selected CM record started after the first dose date of B/F/TAF (including both phases) and on or prior to last dose of B/F/TAF (including both phases). (2) for subjects who meet criteria (1) above, if they took lipid modification medications at first dose of B/F/TAF (including both phases), or if they took lipid modifying medications on or after randomized phase first dose and before first dose of B/F/TAF, they will NOT be considered initiated lipid modifications while receiving B/F/TAF for the all B/F/TAF analysis.
- 20) For figures, if at a visit where n (sample size) for any treatment group <= 5, data for that treatment group will not be displayed at the visit in figure (except the Kaplan-Meier figure), but all data will be included in the corresponding table summary.
- 21) Vital signs and weight, height, BMI will be in the same listing.

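### For subjects switching to open-label B/F/TAF, SAP 3's start-date filter contradicts the SAP's own rules on concomitant medications, lipid drugs and AEs that stop treatment, and no precedence is stated

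*SAP*

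**What the plan says.** **Inclusion rules.** SAP 3 (All B/F/TAF Analysis) treats the two routes to B/F/TAF differently. Where B/F/TAF was the blinded treatment, the rule is that "all available data collected from both randomized phase and OL extension phase (if applicable) will be included in the all B/F/TAF analysis". By contrast, for those who took DTG + F/TAF and then at least one open-label B/F/TAF dose, it admits "all available AE, concomitant medication, pregnancy, and death data with start date" on or after the first open-label dose. The one stated exception lets earlier data supply baseline values. SAP 3.2, describing the pooled All B/F/TAF group, uses collection date: "Only data collected on and after the first dose date of B/F/TAF may be included".

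**Table rules for the same analysis.**

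- SAP 7.4.2 treats a medication with complete dates as concomitant when "the start date is not after last dose date and the stop date is not before first dose date", and an unfinished one as concomitant when "the non-ARV medications are marked as ongoing and start date is on or before last dose date". It ties these dates to the All B/F/TAF first and last dose.
- SAP 7.2.3 plans a count of subjects on lipid-modifying drugs at first B/F/TAF dose. For this, Appendix 8 item 19 requires "any selected CM record with the start date ≤ the first dose date of B/F/TAF (including both phases", with use ongoing or ending on or after that dose. Item 19 also refuses to count a subject as an initiator if already treated at that dose, or "if they took lipid modifying medications on or after randomized phase first dose and before first dose of B/F/TAF".
- SAP 7.1.5.1 gives two routes to treatment-emergent status. The second is "Any AEs leading to premature discontinuation of study drug", with no limit on onset. SAP 3 states that study drug in this analysis means B/F/TAF.

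**The concern.** A start date is a reasonable filter for new events. It is a poor one for drug use, which is a state that can begin long before the period of interest. A statin begun before the switch and taken throughout open-label treatment is concomitant with B/F/TAF, yet its record starts too early to pass SAP 3.

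Two things are at stake. First, columns shown side by side may follow different rules: the B/F/TAF column keeps drugs begun before first dose, the switcher column does not, and the pooled column mixes them. Second, an AE that began on DTG + F/TAF and later ended B/F/TAF may fall between two tables. SAP 3 removes it from the All B/F/TAF table of AEs leading to discontinuation. The randomized-phase version does not take it either, because study drug there is the blinded drug, which the AE did not stop. The disposition summary in SAP 4.1.2 would still count the extension-phase stop and its reason.

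**Working it through.** The plan gives no figure to reproduce, so the check applies each rule to test records for one switcher. Day 0 is the first open-label B/F/TAF dose. Day 672 is the last (96 weeks × 7, the longest extension; illustrative).

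- SAP 3: start ≥ 0.
- SAP 7.4.2: start ≤ 672, and ongoing or end ≥ 0.
- Item 19, use at first dose: start ≤ 0, and ongoing or end ≥ 0.
- SAP 7.1.5.1: onset from 0 to 672 + 30 = 702, or the AE stops B/F/TAF.

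| Medication record | SAP 3 | SAP 7.4.2 | Item 19, at first dose |
|---|---|---|---|
| Day −200, ongoing | out | in | yes |
| Day −200 to 50 | out | in | yes |
| Day −200 to −10 | out | out | no |
| Day 0, ongoing | in | in | yes |
| Day 30 to 60 | in | in | no |
| Day 30, ongoing | in | in | no |

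| AE | SAP 3 | SAP 7.1.5.1 |
|---|---|---|
| Onset day −20, stops B/F/TAF | out | treatment-emergent |
| Onset day −20, does not stop it | out | not treatment-emergent |
| Onset day 0, does not stop it | in | treatment-emergent |
| Onset day 10, stops B/F/TAF | in | treatment-emergent |

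The rules conflict in three rows: the first two medication rows and the first AE row. Elsewhere SAP 3 agrees with 7.4.2 and 7.1.5.1.

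**Lipid row.** SAP 3 needs start ≥ 0 and item 19 needs start ≤ 0. Together they leave only start = 0, that is, a record opening on the day of the first open-label dose.

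**Initiators.** Take a statin record from day −200 to day 50, followed by a second record after a dose change. With all records available, item 19 sees use at first dose and does not count an initiator. If SAP 3 has already removed the first record, only the second remains. It starts after first dose, so the subject counts as an initiator.

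**Size, by assumption only.** The documents give neither the number of switchers *m* nor their medication use. For the first-dose lipid row, if a share *p* of both groups is on such a drug and the switcher column falls to about zero, the pooled figure is p × n / (n + m). Assume p = 20% and n = 283 (about half of the 565 in SAP Appendix 3; the split by arm is not given):

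- m = 50: 0.20 × 283 / 333 = 17.0%
- m = 67: 0.20 × 283 / 350 = 16.2%
- m = 140: 0.20 × 283 / 423 = 13.4%

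The middle case is half of the 49 + 85 = 134 subjects outside the US in Appendix 3. It assumes that only those countries qualify for the extension and that all eligible subjects enter it. The other two values of *m* are arbitrary.

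**The case against.** The strongest reply is that SAP 3 is a general section and the sections defining each table should govern. SAP 7.4.2 names the All B/F/TAF dose dates. Item 19's bar on counting earlier users as initiators has a purpose only for switchers and works only with their pre-switch records. A programmer following those sections would keep the records. The intent is therefore fairly clear, and this part of the reply stands: the loss is conditional.

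It does not remove the contradiction. The SAP 3 rule carries no allowance for exceptions specified elsewhere, although the sentences on tests and listings in the same section do. SAP 3.2 adds another wording. An inclusion rule of this kind would naturally be applied when the data are selected, before any table definition is reached.

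The AE route is also narrow. Under Protocol 6.5.2, subjects who stopped blinded drug early cannot enter the extension, so the AE must begin on DTG + F/TAF in someone who stays on treatment, chooses B/F/TAF and then stops because of it. No frequency can be given. Finally, SAP 7 puts safety data from both phases in the listings, SAP 7.1.6 has a listing of AEs leading to discontinuation, and SAP 3.2 confines treatment comparisons to the randomized phase. All of this stands and limits the consequence.

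**Conclusion.** The contradiction is real and should be settled before the final tables are programmed, because two programmers working from this SAP could produce different All B/F/TAF safety tables. Only the switcher and pooled columns are exposed. Those summaries are descriptive, and the Week 48 primary analysis and the randomized-phase comparisons do not use the rule.

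Three stronger readings are tempting and not supported. One is that these records are certain to disappear: they do so only if SAP 3 is applied ahead of the table-specific sections. The second is that switchers' concomitant medication use would be near zero throughout. That could describe the first-dose lipid row, but SAP 7.4.2 counts use from Study Day 1 to last dose, so drugs started during open-label treatment remain. The third is that the pooled shortfall has a known size. The 13.4% to 17.0% illustration rests on assumed values for the switchers, the B/F/TAF group and the 20% prevalence, and it does not carry over to the wider medication table.

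**What to change.** Amend SAP 3 (All B/F/TAF Analysis) and SAP 3.2 together, so that neither leaves a competing rule:

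1. Take concomitant medication out of the start-date and collection-date rules. For switchers, include every record that meets the SAP 7.4.2 overlap rule relative to first and last B/F/TAF dose.
2. State that all earlier medication records are available for the item 19 checks of use at first dose and prior use.
3. Keep the on-or-after rule for other AEs, pregnancy and death, but add any AE that leads to premature discontinuation of B/F/TAF, whatever its onset, to match SAP 7.1.5.1.

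The cost is a few sentences in two sections and one changed dataset filter. No new data are needed. SAP 1 says that the SAP is finalized before the database, so that is the point at which to settle this.

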### 3.1. Analysis Sets

Analysis sets define the subjects to be included in an analysis. Analysis sets and their definitions are provided in this section. Subjects included in each analysis set will be determined before data finalization. The analysis set will be included as a subtitle of each table, figure, and listing. A summary of the number and percentage of subjects in each analysis set will be provided by treatment group and in total.

## 3.1.1. Analysis Sets Used for the Randomized Phase Analysis

#### 3.1.1.1. All Randomized Analysis Set

The **All Randomized Analysis Set** will include all subjects who are randomized into the study. This is the primary analysis set for by-subject listings.

#### 3.1.1.2. Full Analysis Set

The **Full Analysis Set (FAS)** will include all subjects who (1) are randomized into the study and (2) have received at least 1 dose of blinded randomized study drug. Subjects will be grouped according to the treatment to which they were randomized. For the FAS, all efficacy data collected in the randomized phase, including data collected after the last dose of blinded study drug and on or prior to the first dose date of the OL study drug (if applicable), will be included, unless specified otherwise. This is the primary analysis set for efficacy analyses.

# 3.1.1.3. Per Protocol Analysis Set

The Week 48 **Per Protocol (PP) Analysis Set** will include all subjects who (1) are randomized into the study, (2) have received at least 1 dose of blinded randomized study drug, and (3) have not committed any major protocol violation, including the violation of key entry criteria. Subjects will be grouped according to the treatment they actually received. For the PP analysis, efficacy data up to 1 day after permanent discontinuation of blinded study drug will be included. The Week 48 PP analysis set is the secondary analysis set for efficacy analysis.

Subjects meeting any of the following criteria will be excluded from the Week 48 PP analysis set:

• Subjects who do not have on-treatment HIV-1 RNA in the Week 48 analysis window, except when missing is due to discontinuation of blinded study drug for lack of efficacy. (Note: lack of efficacy is defined as having the check-box for Lack of Efficacy marked as the reason for premature study drug discontinuation (DC) in the "Blinded Treatment" study phase on the study drug completion eCRF page; (Table 1).

Table 1. Subjects Excluded from Week 48 Per Protocol Analysis Set Due to Premature Discontinuation of blinded Study Drug and/or Missing HIV-1 RNA Assessment in Week 48 Analysis Window

Discontinuation from blinded S	Study Drug prior to or on the	HIV-1 RNA Data on Rando in Week 48 An	
Upper Bound of Week 48 Analysis Window		Yes	No
Yes	Due to Lack of Efficacy	+	+
i es	Due to Other Reasons	+	-
No		+	-

+= Inclusion of Subjects in Week 48 PP analysis set; -= Exclusion of Subjects in Week 48 PP analysis set.

- Subjects who do not meet the inclusion criterion of receiving a stable antiretroviral regimen of DTG + F/TAF or DTG + F/TDF for the following duration prior to the screening visit:1) ≥ 6 months (if there is documented or suspected NRTI resistance), or 2) ≥ 3 months (if there is no documented or suspected NRTI resistance)
- Subjects who do not meet the inclusion criterion of having documented plasma HIV-1 RNA
   < 50 copies/mL during treatment with DTG+F/TAF or DTG+F/TDF (for a minimum period of ≥ 6 or ≥ 3 months, as applicable) preceding the screening visit (or undetectable HIV-1 RNA level according to the local assay being used if the limit of detection is ≥ 50 copies/mL)

- Subjects who do not meet the inclusion criterion of having HIV RNA-1 < 50 copies/mL at the screening visit
- Subjects who do not meet the inclusion criterion of having no documented resistance to INSTIs or confirmed virologic failure (2 consecutive HIV-1 RNA ≥ 50 copies/mL after achieving < 50 copies/mL while on an INSTI-containing regimen)

- Subjects who do not meet the inclusion criterion of only having the following permitted historical ARV resistance:
  - 1) Any NRTI resistance mutations
  - 2) Any non-nucleoside reverse transcriptase mutations
  - 3) Any protease inhibitor mutations
  - 4) Subjects with resistance to 2 or more classes of antiretrovirals must be reviewed by the Gilead medical monitor to confirm eligibility
- Subjects who meet the exclusion criterion for receiving ongoing therapy with any of the medications listed in the table in Section 4.3 of the protocol including drugs not to be used with BIC, FTC, TAF and DTG
- Nonadherence to study drug: subjects with adherence rate for active study drug up to the Week 48 Visit below the 2.5th percentile

